The primary aim is to evaluate the effects of standard PT compared to PT with SWT, PT with PBMT, and PT with a combination of SWT and PBMT in the management of AT. *We hypothesize servicemembers in each treatment allocation will see improvement in functional outcomes, pain and measures of Achilles tendon structure compared to baseline measures. As SWT and PBMT may change structural properties and modulate pain in tendinopathy, we anticipate greater measures in activity function for participants assigned to SWT and PBMT over PT as sole treatment.*

The secondary outcome will be to evaluate cross-over response. After the initial 3-month randomized control trial, participants who are not satisfied with results will be able to select a different treatment arm for the remaining 3 months of the study.

9.4 Study Design:

Describe study design in one to two sentences (e.g., prospective, use of existing records/data /specimens, observational, cross-sectional, interventional, randomized, placebo-controlled, cohort, etc.). Specify the phase – Phase I, II, III, or IV – for FDA-regulated investigational drug research

A Randomized Control Trial with Elective Cross-Over Design

9.5 Target Population:

Describe the population to whom the study findings will be generalized

Active-Duty Service Members (ADSMs) and the active civilian runner population

9.6 Benefit to the DoD:

State how this study will impact or be of benefit to the Department of Defense

AT is a common overuse running injury among ADSMs that can impact their combat readiness throughout their military career. Current rehabilitation treatment plans include ECC, but its success rate is limited leaving approximately 40% without full relief of pain and symptoms and decreased activity levels. The use of SWT, PBMT, or both SWT and PBMT along with physical therapy on ADSM with AT, may improve their recovery time. Faster healing translates to quicker return to higher level activities, return to duty (RTD), and ultimately mission ready status.

10.0

Study Procedures, Data Management, and Privacy

10.1 Study Procedures:

Describe step-by-step how the study will be conducted from beginning to end

The study procedures will take place in the Physical Therapy, Sports and Exercise Medicine, and Orthopaedic and Podiatry Clinics.

Recruitment, Pre-Screening (before consent), Study Introduction & Informed Consent:

Potential participants will be identified via four methods:

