12.4 Special categories, check all that apply

- Minors /Children
- Students
- Employees - Civilian
- Employees - Contractor
- Resident/trainee
- Cadets /Midshipmen
- Active Duty Military Personnel
- Wounded Warriors
- Economically Disadvantaged Persons
- Educationally Disadvantaged Persons
- Physically Challenged (Physical challenges include visual and/or auditory impairment)
- Persons with Impaired Decisional Capacity
- Prisoners
- Pregnant Women, Fetuses, and Neonates
- Non-English Speakers
- International Research involving Foreign Nationals - Headquarters Review is necessary

You must also consider the requirements of DoDI 3216.02, Enclosure 3, paragraph 7.e.

12.5 Inclusion Criteria:

Order Number	Criteria
1	DEERs Eligible
2	Between ages of 18-64 (inclusive) years old
3	Currently AD in any of the US Armed Forces
4	Clinical diagnosis of mid-portion Achilles tendinopathy (including both unilateral and bilateral) by a healthcare provider based on accepted diagnostic criteria
5	Able to read and understand English language for consent purposes
6	Able to commit to 3-weeks of intervention and 6-months of follow-up

12.6 Exclusion Criteria:

Order Number	Criteria
1	Primary insertional Achilles tendinopathy
2	Platelet Rich Plasma (PRP), corticosteroid injection, or prolotherapy within 3 months
	Received dry needling within the past 4 weeks

3	
4	Previously completed the Silbernagel protocol for Achilles tendinopathy within the past 3 months
5	Received SWT within the past 3 months to their Achilles
6	Tattoo in the area of treatment (due to sensitivity to PBMT)
7	Current use of pacemaker
8	Patients with a known underlying cardiac disease that could be affected by shockwave therapy
9	Patients with neuropathy affecting sensation to pain
10	Current use of medications associated with sensitivity to heat or light (e.g., amiodarone, chlorpromazine, doxycycline, hydrochlorothiazide, nalidixic acid, naproxen, piroxicam, tetracycline, thioridazine, voriconazole)
11	Current or chronic sciatica (lumbosacral radiculopathy) resulting in chronic or intermittent lower extremity pain, numbness, or tingling
12	Achilles tendon tear or prior Achilles tendon surgery
13	Recent lower extremity injury within the last 3 months that required professional medical attention (e.g., ankle sprain, meniscus)
14	Concurrent participation in another research study addressing pain issue
15	Previously enrolled in the study for contralateral (opposite) leg

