16	Currently pregnant or plan to become pregnant during intervention period (safety of PBM not established in pregnancy) as determined by hCG urine test
17	Diagnosis of rheumatological disease/connective tissue condition, symptomatic arthritis of foot and ankle, a primary running related injury outside Achilles tendinopathy, other contraindications to PBMT or SWT

13.0

Recruitment and Consent

13.1 Please describe the recruitment process, including how subjects will be identified and selected for the study.

Potential participants will be identified via four methods:

- Under the provisions of an approved Partial HIPAA Waiver Application for this study, the local study team members will review medical records of patients coming in to the Sports Medicine, Physical Therapy, Orthopedic, Podiatry, and Physical Medicine & Rehabilitation (PM&R) clinics, for suspected/confirmed AT in order to identify prospective research participants and to seek their authorization to participate/use their protected health information for this research study. The study team will receive approval from the potential participant's provider prior to approaching for possible study participation.
- Direct referral from local healthcare providers in the local Sports Medicine, Family Medicine, Orthopedic and Podiatry, Physical Therapy, Holistic Health and Fitness (H2F), and Physical Medicine & Rehabilitation (PM&R) clinics.

3. Patients may self-refer to participate in the study. Interested potential participants will be able to contact a member of the study

team via email. Potential participants who contact the study team directly will be instructed to seek care with the Physical Therapy or their primary care manager for a physical exam and diagnosis of AT, or confirmation of a previous AT diagnosis. The Physical Therapy Clinic is a direct access clinic that does not require a referral.

4. Study advertisements will be posted within the following locations, and copies will be provided to clinic staff:

- Internal Medicine
- Aviation Medicine
- H2F
- McChord Clinic
- Winder Clinic
- Okubo SCMH
- Allen Soldier -Center Medical Home
- SRU
- Puyallup Community Medical Home
- South Sound Community Medical Home
- Armed Forces Wellness Center
- Intrepid Spirit Center
- Madigan Medical Mall
- Pharmacy waiting areas, if possible
- Physical Therapy
- Podiatry
- Sports Medicine
- THOR3
- Physical Medicine and Rehabilitation
- Coffee bar
- Dining Facility entrance
- Intranet screen saver page

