The potential risks directly associated with study-specific activities and procedures are minimal.

Physical Therapy (PT)

Possible risks associated with physical therapy treatment include: worsening of pre-existing conditions, continued and/or increased pain that may limit activities, no improvement in mobility or strength, soreness, or failing during and/or injury from physical therapy exercises and/or performance-based tests.

Research Procedure: Shockwave Therapy (SWT)

The OrthoPlus Ultra 100 is a Class I FDA approved device with minimal risk. It is a low energy device and no severe events have been reported. Reported discomforts of shockwave include bruising, swelling and rarely, tissue damage. Pain response is expected due to device treatment over sites of injury and use of process of clinical focusing; we will monitor each participant and adjust treatment settings to ensure pain is tolerable during the treatment. Participants may stop the SWT at any time.

Research Procedure: Photobiomodulation (PBM) Therapy

The risks associated with PBMT are minimal. PBM treatment is used by a variety of healthcare practitioners for painful clinical conditions. Mild discomfort may be experienced during the treatment, the treatment should not be "hot", but participants should notify the study team member if they feel any uncomfortable warming. Individuals with neuropathies or difficulty distinguishing changes in skin temperature are at higher risk. Potential research-related risks include damage to eye structures and skin, which are both very rare.

Additionally, any time information is collected for a study, there is a small risk of breach of confidentiality.

14.2

Measures to Minimize Risks of Harm (Precautions, safeguards):

For each research procedure or intervention, describe all measures to minimize and/or eliminate risk of harms to subjects and study personnel

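### Prior shockwave to the Achilles is washed out for 3 months before entry, but prior PBMT, the other randomised add-on, has no look-back at all

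*Combined protocol and SAP*

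**What the plan says.** Four of the exclusions in Section 12.6 are look-back rules for earlier treatment:

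- item 2: "Platelet Rich Plasma (PRP), corticosteroid injection, or prolotherapy within 3 months"
- item 3: "Received dry needling within the past 4 weeks"
- item 4: "Previously completed the Silbernagel protocol for Achilles tendinopathy within the past 3 months"
- item 5: "Received SWT within the past 3 months to their Achilles"

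PBMT appears in the same list only on safety grounds. Item 6 begins "Tattoo in the area of treatment (due to sensitivity to PBMT", item 16 concerns pregnancy, and item 17 ends with "other contraindications to PBMT or SWT". No item mentions earlier PBMT or laser treatment.

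Section 9.3 states the comparison of interest: "The primary aim is to evaluate the effects of standard PT compared to PT with SWT, PT with PBMT, and PT with a combination" of the two. Section 10.1 randomises to four groups, two of which receive PBMT. Section 11.2 bases its power assumptions on PT + PBMT against PT only.

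**The concern.** The protocol itself supplies three treatment components: the home loading programme, SWT and PBMT. Recent use of the first two is screened out and recent use of the third is not, and no reason is given. Section 9.2 regards PBM as active in this condition. Sections 11.1 and 11.6 cite the lack of a washout before Part 2 as one reason to make that analysis exploratory. The same reasoning is applied at entry to SWT but not to PBMT.

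A patient who finished laser treatment to the same tendon shortly before screening is thus eligible, and may be assigned to PT only or to an arm that repeats PBMT. In such patients PT + PBMT versus PT compares a repeat course with no repeat course, both after recent treatment. It no longer measures adding PBMT to PT in someone not recently treated. The PBMT component of the combination arm is affected in the same way. Prior SWT within 3 months is excluded, so the two add-on contrasts do not start from the same footing.

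**Working it through.** **1. Does any other text close the gap?**

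- Section 12.6, items 14 and 15, bar concurrent pain research and re-enrolment for the other leg. Neither covers PBMT received in ordinary care.
- Section 12.6, item 17, covers contraindications. Earlier use is nowhere described as one.
- Sections 10.1 and 13.3 refer eligibility to the listed criteria and the Inclusion/Exclusion CRF and add no PBMT rule.
- Section 10.14 allows relevant treatment history to be taken from the record, and Section 11.1 allows optional adjustment for relevant clinical variables. Neither names PBMT, and neither keeps recent users out.

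Eligibility is settled before randomisation, so recent users can fall in any arm.

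**2. The plan's own power figures.** Section 11.2 gives 90% power for 16 points at 35 per arm, 17 at 30 and 18 at 25. Alpha is 0.05, two-sided (Section 11.6). The SD is not stated, so it is solved back by normal approximation:

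SD = difference / [(1.960 + 1.282) × √(2/n)]

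| n per arm | Difference | Implied SD |
|---|---|---|
| 35 | 16 | 20.65 |
| 30 | 17 | 20.31 |
| 25 | 18 | 19.63 |

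A single SD of 20.2 returns power of 91.2%, 90.3% and 88.3%, so the three scenarios agree to within 2 points of 90%. This is a consistency check; the SD itself cannot be verified from the documents.

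**3. Dilution.** Let p be the share of patients with recent PBMT, and let a repeat course add a fraction r of the full effect in them. For a true difference of 16 points the expected contrast is

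16 × [(1 − p) + p × r]

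The worst case is r = 0, which gives 16 × (1 − p). The documents give neither p nor r, so both are assumptions. Power is Φ(contrast / [20.2 × √(2/35)] − 1.960), and 20.2 × √(2/35) = 4.83.

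| p | Contrast, r = 0 | Power | Contrast, r = 0.5 | Power |
|---|---|---|---|---|
| 0 | 16.0 | 91.2% | 16.0 | 91.2% |
| 5% | 15.2 | 88.3% | 15.6 | 89.8% |
| 10% | 14.4 | 84.7% | 15.2 | 88.3% |
| 20% | 12.8 | 75.5% | 14.4 | 84.7% |

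At the minimum final sample of 28 per arm the standard error is 20.2 × √(2/28) = 5.40. For the same 16 points, power is about 84% with no dilution, 76% at p = 10% and 66% at p = 20% (r = 0).

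**4. Chance imbalance.** The SD of the between-arm difference in the share of recent users is √[2p(1 − p)/28] at 28 per arm. This is 5.8, 8.0 and 10.7 percentage points at p = 5%, 10% and 20%.

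**The case against.** The strongest reply is that the problem may be negligible. The only text on how widely PBM is used is a general remark in Section 14.1: "PBM treatment is used by a variety of healthcare practitioners for painful clinical conditions". It says nothing about Achilles tendons, this site or the months before screening. At p = 5% only 0.05 × 28 = 1.4 patients per arm would be affected. That reply stands as to size. It does not explain why SWT is screened and PBMT is not.

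Several stronger readings are tempting, and the documents do not support them:

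- **That the comparison is biased or confounded.** Prior use precedes randomisation and is balanced in expectation. What remains is dilution and chance imbalance.
- **That recent users who enrol are those PBMT failed.** No passage supports this, and it would also leave little benefit to carry over.
- **That PT only is improved by leftover benefit.** The outcome is change at 3 months, so benefit present at entry is already in the baseline score. The net effect could go either way, depending on how long the benefit lasts.
- **That 16 points is the planned effect.** It is the difference detectable with 90% power at 35 per arm, one of three scenarios.

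It is also fair to say that look-back windows need not be equal. The protocol itself uses 4 weeks for dry needling and 3 months elsewhere, Section 9.2 gives SWT and PBMT different mechanisms, and nothing states how long PBMT effects last. That is an argument about the length of a window, not a reason to have none. Appendices A, D and O are not in the supplied text and may ask about prior laser treatment, but Section 12.6 as written would not exclude anyone on the answer.

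Finally, Section 10.1 lets the standard-care provider use other modalities during Part 1 in every arm. An entry rule does not close that route.

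**Conclusion.** The point holds as an unexplained asymmetry in the entry criteria that is cheap to remove. As written, recent PBMT users are eligible for all four arms, which can dilute the PBMT contrasts and add chance imbalance. The magnitude cannot be established. The worst-case illustration, a loss of 0.8 to 3.2 points from a 16-point difference for p between 5% and 20%, rests on an assumed prevalence, no gain at all from a repeat course, and an SD solved back from the plan's own scenarios. If a repeat course retains half the effect, the loss halves. If recent PBMT is rare in the recruiting clinics, the effect is close to nil. The plan's stated power figures are not in dispute.

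**What to change.** Bring the PBMT entry rule into line with the SWT rule by adding recent PBMT or laser treatment to the Achilles to the exclusions in Section 12.6. The protocol's existing SWT window is the natural default, but the study team should set the length, since the documents do not say how long PBMT effects last. If the omission is deliberate, state the reason. Make matching changes to the Inclusion/Exclusion CRF (Appendix A) and the Screening Script (Appendix O).

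For participants already enrolled, record prior PBMT (yes/no, with date) from the medical record, to which Sections 10.9 and 10.14 already provide access. Prespecify a sensitivity analysis that repeats the PBMT contrasts without recent users.

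The cost is one line of criteria, one screening question, a short record check and a small loss of otherwise eligible patients.

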
13.5 DoDI 3216.02 requires an ombudsman to be present during recruitment briefings when research involves greater than minimal risk and recruitment of Service members occurs in a group setting. If applicable, you may nominate an individual to serve as the ombudsman.

- N/A
- Propose ombudsman

13.6 Withdrawal from Study Participation:

Explain the process for withdrawal and specify whether or not the subjects will be given the opportunity to withdraw their data their data/specimens in the event they wish to withdraw from the study

Participant Withdrawal:

Participants may withdraw from the study at any time without penalty. Participants will be informed that withdrawal will not affect their access to health care that they are otherwise entitled to and it will not affect their military position.

If a participant withdraws from the study, we may retain and analyze all coded/de-identified data collected up to the time of withdrawal if the data is necessary to maintain the integrity of the study. However, no further data will be collected after the date of withdrawal.

Participants may contact the study research coordinator/assistant or Principal Investigator to formally withdraw from the study. Participants will be advised to follow-up with their personal physician if they choose to withdraw.

Withdrawal Without Participant Consent:

Participants will be withdrawn if they fail to meet the formal screening criteria outlined in protocol section 13.3.

Additionally, a participant may be withdrawn from the study without their consent if remaining in the study might be dangerous or harmful to them. Participation may also be stopped if the military mission requires it, if they lose their right to receive medical care at a military hospital, if the study is canceled, if they fail to adhere to the protocol and/or therapy plan, or if they display inappropriate behavior towards study personnel.

The reason for any withdrawal/removal will be documented.

14.0

Risks and Benefits

14.1

Risks of Harm:

Identify all research-related risks of harm to which the subject will be exposed for each research procedure or intervention as a result of participation in this study. Consider the risks of breach of confidentiality, psychological, legal, social, and economic risks as well as physical risks. Do not describe risks from standard care procedures; only describe risks from procedures done for research purposes

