15.1 Your study requires either Data and Safety Monitoring Plan (DSMP) or a Data and Safety Monitoring Board (DSMB).

- DSMP
- DSMB
- Both
- Not Applicable

A DSMP should describe the plan to monitor the data to verify that the data are collected and analyzed as specified in the protocol. Include who will conduct the monitoring, what will be monitored, and the frequency of monitoring. It should also include the plan to ensure the safety of subjects

Participant Safety Monitoring Plan:

To ensure the safety of participants the PI will:

1. Monitor the conduct of the protocol per the approved study plan and ensure protection of human participants. This may involve periodic review of medical records and/or research files of enrolled participants.
2. Review and keep abreast of adverse events and protocol deviations that occur during the research.
3. The PI will review and sign adverse event logs/reports, protocol deviation logs/reports, and continuing reviews/annual progress reports.
4. If there is concern about the welfare of enrolled participants, the PI will stop the research study in progress, remove individual participants from a study, and take whatever steps necessary to protect the safety and well-being of research participants until the IRB can assess the situation.
5. Ensure that all study team members keep current required human subjects research trainings which require renewal every 3 years.

If an adverse event or protocol deviation occurs, it will be evaluated by the Principal Investigator and appropriate actions will be taken as outlined in Section 16.0 Reportable Events. In the case of an emergency, first responders will be called. In order to address the challenge of early identification of an increased risk of a known adverse event, all adverse event data will be tracked and evaluated.

On-site physicians will monitor the progress and health of the participants alongside our Principal Investigator. Participants can elect to withdraw from the study at any time. Participants may also be taken out of the study at any point if a research provider (or one of their treating providers)

determines that it is no longer safe for them to continue with the study. If a participant elects to drop out of the study or is withdrawn for safety reasons, they will resume standard of care treatment with their assigned health provider(s).

Data Monitoring Plan:

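### Section 13.6 ends data collection at voluntary withdrawal with no exception for adverse events, and is silent on data after removal, so the outcome of an ongoing event is not collected once a participant leaves

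*Combined protocol and SAP*

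**What the plan says.** Section 13.6 treats two routes out of the study under separate subheadings.

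- **Voluntary withdrawal.** On earlier data the plan says "we may retain and analyze all coded/de-identified data collected up to the time of withdrawal", if they are needed for the integrity of the study. It then says "However, no further data will be collected after the date of withdrawal". On care, it says "Participants will be advised to follow-up with their personal physician if they choose to withdraw".
- **Removal without consent.** Among other grounds, "a participant may be withdrawn from the study without their consent if remaining in the study might be dangerous or harmful to them". Nothing is said about data after removal.
- **Record of the reason, placed at the end of the section.** "The reason for any withdrawal/removal will be documented".

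Section 15.1 sets out safety monitoring. To identify early an increased risk of a known event, it says "all adverse event data will be tracked and evaluated". For leavers it says "If a participant elects to drop out of the study or is withdrawn for safety reasons, they will resume standard of care treatment".

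Sections 10.1 and 14.2 have adverse events looked for at check-ins and follow-up visits. Section 16.1 has the principal investigator determine the severity of each event and its relationship to the research. It sets reporting deadlines that run from discovery.

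**The concern.** A participant who leaves because of an adverse event is one whose later course matters for judging safety. As 13.6 is written, the study holds the event as it stood at exit but does not collect whether it resolved, persisted or worsened. It also does not look for a treatment-related event that appears afterwards.

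Two things are at stake. The principal investigator's view of severity and relationship, and of whether there is a wider welfare concern under 15.1, rests on an incomplete picture for these participants. The loss is also unlikely to be random: leaving because of pain, or being removed because staying could be harmful, selects for participants with events. Section 14.1 expects pain during shockwave treatment, so the loss could differ by arm, although the documents give no rate.

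**Working it through.** No figure in the plan is at issue, so the check sets the relevant sections side by side.

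**1. Is there an exception for adverse events?** None was found in 13.6, 14.2, 15.1 or 16.1. The sentence in 13.6 is general and so covers safety data.

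**2. Does another section supply the follow-up?**

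| Section | What it provides | What it gives for a leaver |
|---|---|---|
| 10.1, Follow-Up Data Collection | Check-ins twice weekly for three weeks; adverse event evaluation at each follow-up time point (3 weeks, 6 weeks, 3 months, 6 months) | Nothing after exit |
| 14.2 | Adverse event evaluation at each follow-up visit; all events go to the principal investigator | Nothing after exit |
| 13.6 and 15.1 | Advice to see own physician; return to standard of care | Clinical care, with no stated return of information to the study |
| 16.1 | Reporting deadlines from discovery | A duty to report what becomes known, with no duty to follow an event to resolution |

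**3. What is kept?** Data up to withdrawal may be retained, the reason is documented, and all events go to the principal investigator. The event that leads someone to leave is therefore captured if it was reported by then.

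**4. Is stopping treatment the same as leaving?** No. Section 14.1 lets participants stop shockwave therapy at any time. Section 14.2 allows either device treatment to be modified or stopped because of discomfort. Part 2 in section 10.1 lets participants decline further treatment but still requires the 6-month visit. None of these ends participation, so the gap concerns only those who leave the study.

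**5. What would a leaver miss?** Section 10.1 schedules ultrasound at baseline, 3 months and 6 months, and the examination annotates Achilles tears. Someone who leaves during the three treatment weeks misses both later scans and the 6-week, 3-month and 6-month adverse event evaluations.

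**6. Can the number affected be derived?** Section 11.2 goes from 160 enrolled to a final sample of at least 112: 160 − 112 = 48, and 48/160 = 30%. That allowance combines screen failures with attrition and is not split. Nothing says what share of the attrition would be due to harm, so the 30% does not measure this problem.

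**The case against.** The strongest case for leaving 13.6 alone has four parts.

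- **Autonomy.** Ending collection when someone chooses to leave respects that choice, which matters among active-duty personnel. This stands, and it is why follow-up should be by permission only.
- **Low risk and a short course.** Section 16.1 describes the study as minimal risk, and device treatment in Part 1 lasts three weeks. This lowers the expected number of events. It does not remove the value of knowing how one ended.
- **The harm is already captured, and treatment can be stopped without leaving.** Both are true. A reader might infer that the plan loses the harms themselves, or that anyone who cannot tolerate treatment drops out of safety follow-up. The documents support neither reading.
- **The consent form or HIPAA authorization may cover it.** Neither was available to check. Even if one does, 13.6 should agree with it.

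A reader might also take the stop on data as applying to participants removed for harm. The sentence sits under voluntary withdrawal only; for removal the plan is silent, which is an omission and not a prohibition. Nor can it be said that a later event could never reach the study. An event the team happened to learn of might fall under the from-discovery rules in 16.1, and 13.6 does not say how the two interact.

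**Conclusion.** The concern holds in a limited form. After voluntary withdrawal the stated rule leaves the outcome of an ongoing adverse event, and any later treatment-related event, uncollected. After removal without consent the plan does not say what happens. Both sit poorly with the tracking commitment in 15.1 and the determination required by 16.1.

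The size is unknown. A reader might try to derive it from the 28 per arm in the final sample, reasoning that completers could show no events. That does not follow: the complete-case rule in section 11.1 belongs to the outcome analysis, and no section restricts adverse event reporting to completers. Events logged before exit can still be counted. What is lost is their course, not their occurrence.

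The conclusion assumes that 13.6 is applied as written and that the consent and authorization documents do not already provide for safety follow-up. It is a modest, inexpensive improvement to the safety data and does not affect the primary efficacy analysis.

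**What to change.** In 13.6, for both withdrawal routes, separate leaving the study from declining safety follow-up. At exit, ask whether the team may follow any ongoing or possibly treatment-related adverse event to resolution or the planned 6-month date, by remote contact or record review. If the participant declines, stop all collection.

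Add matching wording to the consent form and the HIPAA authorization. Authority for record review after exit should not be presumed from what is described: the 3-month chart review in section 10.1 is for physical therapy visits, and the partial HIPAA waiver is for identifying recruits. Participants removed after failed contact attempts cannot be asked at exit, so the consent wording should state what applies to them.

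Align 15.1 and 16.1 with the revised 13.6, including how an event learned of after withdrawal is handled.

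The cost is protocol, consent and authorization wording, a small burden on leavers (who may refuse), and a brief contact by existing staff. Section 10.1 already allows remote data capture, and 13.4 already foresees sending new findings to past participants. No treatment or visit schedule changes.
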